4.6.5. Electrocardiograms

Summary statistics by treatment and by nominal visit will be provided for ECG parameters (heart rate, PR, QRS, RR, and QT corrected using QTcF). When the QRS is prolonged (eg, a complete bundle branch block), QTcF should be used to assess ventricular repolarization. Thus, for a particular ECG, the following will be set to missing (for analysis purposes) when QRS is 120 msec or longer: QT and QTcF. Change from baseline to postbaseline values for ECG parameters will be summarized for patients who have both a baseline and at least 1 postbaseline result. Only planned measurements will be included in the mean change analyses. The criteria for identifying participants with treatment-emergent quantitative ECG abnormalities is based on [Table GZBF.4.7](#). The counts and percentages of participants who meet following criteria at any time during the entire study period (including the off drug follow up time period) will be summarized by treatment group:

- treatment-emergent ECG abnormalities as listed in [Table GZBF.4.7](#)
- PR greater than or equal to 220 msec with 0% through 25% and higher than 25% increase from baseline
- QTcF greater than 500 msec, and
- treatment-emergent increase from baseline in QTcF interval of greater than 30 msec, 60 msec, or 75 msec.

Treatment-emergent qualitative ECG abnormalities are defined as qualitative abnormalities that first occurred after baseline. A listing of abnormal qualitative ECGs will be created (see).

Table GZBF.4.7. Selected Categorical Limits for ECG Data

Parameter	Low		High	
	Males	Females	Males	Females
Heart Rate (bpm)	<50 and decrease ≥ 15	<50 and decrease ≥ 15	>100 and increase ≥ 15	>100 and increase ≥ 15
PR Interval (msec)	<120	<120	≥ 220	≥ 220
QRS Interval (msec)	<60	<60	≥ 120	≥ 120
RR Interval (msec)	<300	<300	>1714	>1714
QTcF (msec)	<330	<340	>450	>470

Abbreviations: bpm = beats per minute; ECG = electrocardiogram; QTcF = Fridericia's corrected QT interval.

4.6.6. Clinical Laboratory Evaluation

All laboratory data will be reported in SI units. Selected laboratory measures will also be reported using CN units. Limits from the performing lab will be used to define low (L) and high (H). Descriptive summaries by treatment and by nominal visit will be provided for the baseline and postbaseline values as well as the change from baseline values.

Observed and change from baseline values for each visit may be displayed in plots for participants who have both a baseline and at least 1 postbaseline planned measurement. Baseline will be the last nonmissing observation prior to taking first study drug. Unplanned measurements will be excluded from plots.

A shift table will be provided including unplanned measurements. The shift table will include the number and percentage of participants within each baseline category (low, normal, high, or missing) versus each postbaseline category (low, normal, high, or missing) by treatment. The proportion of participants shifted will be compared between treatments using Fisher's exact test.

For qualitative laboratory analytes, the number and percentage of participants with normal and abnormal values will be summarized by treatment.

A listing of abnormal findings will be created for laboratory analyte measurements, including qualitative measures. The listing will include participant identification, treatment group, laboratory collection date, study day, analyte name, and analyte finding.

The MMRM model as described in Section 4.3.2 or ANHECOVA (if MMRM model is not applicable) as described in Section 4.3.3 will be used for the analysis during the treatment period for the continuous measurements for selected lab tests. The ANHECOVA, if used in this case, will use EAS with multiple imputation performed by applying only hypothetical strategy to ICE.

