Treatment effect of interest is thus defined as the difference in mean percent changes in body weight at Week 24 between QW LY3437943 and placebo.

Rationale for “efficacy estimand”: This Phase 2 study aims to study the efficacy of LY3437943 under the ideal condition that all participants adhere to the randomized treatment.

Estimand(s) for Secondary Objectives

The same estimand for the primary objective will be used for the following efficacy endpoints for the secondary objectives:

- difference between LY3437943 and placebo in percent change from baseline in body weight at Week 48
- percentage of participants with 5% or higher, 10% or higher, and 15% or higher body weight loss from baseline at Weeks 24 and 48
- change from baseline in body weight (kg) at Weeks 24 and 48
- change from baseline in BMI (kg/m²) at Weeks 24 and 48; and
- change from baseline in waist circumference (cm) at Weeks 24 and 48.

Unless specified otherwise, safety and tolerability assessments will be guided by an estimand comparing safety of LY3437943 doses with placebo for the whole study period (the treatment period plus safety follow-up period) irrespective of adherence to study intervention for all study population (including inadvertent enrollment).

Supplemental Estimand(s) for Primary Efficacy Endpoint

An alternative estimand, called “hybrid estimand”, is the mean treatment difference in percent change in body weight from baseline at Week 24 between LY3437943 and placebo in participants who meet the inclusion criteria with ICEs handled differently according to the reasons for the events:

- Category 1: The ICEs of permanent discontinuation of study drug due to reasons unlikely related to the efficacy/safety outcomes will be handled by the hypothetical strategy.
- Category 2: The ICEs of permanent discontinuation of study drug due to lack of efficacy before study treatment discontinuation will be handled by the hypothetical strategy
- Category 3: All other ICEs will be handled by the treatment policy strategy. With treatment policy strategy, the occurrences of “permanent discontinuation of study drug” is considered irrelevant in defining the treatment effect of interest. The value for the response variable is used regardless of whether or not the ICE occurs.

Population-level summary: mean percent change in body weight at Week 24.

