2.1. Multiplicity Adjustment

No adjustment for multiplicity will be performed.

3. Analysis Sets

For the purposes of analysis, the following analysis sets are defined:

Participant Analysis Set	Description
Entered	All participants who sign the informed consent form.
Randomized	All participants who are randomly assigned to a treatment arm.
Efficacy Analysis Set (EAS)	Data obtained during treatment period from all randomly assigned participants. Excludes participants discontinuing study drug due to inadvertent enrollment and data after discontinuation of study drug. Participants will be analyzed according to the treatment group to which they were randomly assigned.
Full Analysis Set (FAS)	Data obtained during treatment period from all randomly assigned participants who take at least 1 dose of double-blind study treatment, excluding participants discontinuing study drug due to inadvertent enrollment, regardless of adherence to study drug. Participants will be analyzed according to the treatment group to which they were randomly assigned.
Safety Analysis Set (SS)	Data obtained during treatment period plus safety follow-up period from all randomly assigned participants who take at least 1 dose of double-blind study treatment, regardless of adherence to study drug. Participants will be analyzed according to the treatment group to which they were randomly assigned.

4. Statistical Analyses

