4.6. Safety Analyses

Unless specified otherwise, safety assessments will be guided by an estimand comparing safety of LY3437943 doses with placebo irrespective of adherence to study drug. Thus, safety analyses will be conducted using the safety analysis set.

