4.6.4. Vital Signs

In the case that multiple records of an individual vital sign are collected at the same visit, they will be averaged prior to being used for data summaries and analyses.

Descriptive summaries by treatment and by nominal visit will be provided for baseline and postbaseline values as well as change from baseline values.

Treatment differences in mean change will be analyzed using the MMRM model as described in Section 4.1 with all available data in the safety analysis set.

Counts and percentages of participants with treatment-emergent abnormal sitting systolic blood pressure, sitting diastolic, and pulse will be presented by treatment for participants who have both baseline and at least 1 postbaseline result. A treatment-emergent high result is defined as a change from a value less than or equal to the high limit at baseline to a value greater than the high limit at any time that meets the specified change criteria during the postbaseline period. A treatment-emergent low result is defined as a change from a value greater than or equal to the low limit at baseline to a value less than the low limit at any time that meets the specified change criteria during the postbaseline period. To assess decreases, change from the minimum value during the baseline period to the minimum value during the postbaseline period will be used. To assess increases, changes from the maximum value during the baseline period to the maximum value during the postbaseline period will be used. Both planned and unplanned measurements will be included in the analysis. The criteria for identifying patients with treatment-emergent vital sign abnormalities are stated in [Table GZBF.4.6](#).

Table GZBF.4.6. Categorical Criteria for Abnormal Treatment-Emergent Blood Pressure and Pulse Measurements

Parameter	Low	High
Systolic BP (mm Hg) (Supine or sitting – forearm at heart level)	≤ 90 and decrease from baseline ≥ 20	≥ 129 and increase from baseline ≥ 20
Diastolic BP (mm Hg) (Supine or sitting – forearm at heart level)	≤ 50 and decrease from baseline ≥ 10	≥ 90 and increase from baseline ≥ 10
Pulse (bpm) (Supine or sitting)	< 50 and decrease from baseline ≥ 15	> 100 and increase from baseline ≥ 15

Abbreviations: BP = blood pressure; bpm = beats per minute

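### The fallback ANHECOVA for safety laboratory tests uses the efficacy set and a hypothetical strategy, an unexplained exception to the SAP's own safety estimand

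*SAP*

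**What the plan says.** SAP 4.6.6 gives two models for the mean change in selected continuous laboratory tests: the MMRM of Section 4.3.2 or, failing that, "ANHECOVA (if MMRM model is not applicable) as described in Section 4.3.3 will be used for the analysis during the treatment period". For that second model it adds: "The ANHECOVA, if used in this case, will use EAS with multiple imputation performed by applying only hypothetical strategy to ICE". It names no analysis set for the MMRM.

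The efficacy analysis set (EAS) is defined in SAP Section 3: "Excludes participants discontinuing study drug due to inadvertent enrollment and data after discontinuation of study drug". The safety analysis set (SS), in the same table, is wider and applies whether or not participants adhered: "Data obtained during treatment period plus safety follow-up period from all randomly assigned participants who take at least 1 dose of double-blind study treatment".

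The general safety rule opens SAP 4.6: "Unless specified otherwise, safety assessments will be guided by an estimand comparing safety of LY3437943 doses with placebo irrespective of adherence to study drug". It continues: "Thus, safety analyses will be conducted using the safety analysis set". SAP 4.1 repeats this rule. SAP 1.1 states the safety estimand over the treatment and follow-up periods, "irrespective of adherence to study intervention for all study population (including inadvertent enrollment".

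Protocol 7.1 keeps a participant who permanently stops drug in the study for all planned efficacy and safety measures, so these laboratory values are meant to be collected.

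**The concern.** The trial plans to follow people after they stop drug and to judge safety whether or not they adhere. The laboratory ANHECOVA does the reverse. It deletes values taken after drug discontinuation and fills the gap with values imputed as if the person had stayed on drug. Those who stop include people stopping for an adverse event or for a significant calcitonin rise (Protocol 7.1 and 8.3.2.3.1), so the deleted values are not a random subset.

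At stake are the modelled laboratory contrasts, with their confidence intervals and p-values. For a given test these would answer an on-drug question if the fallback is fitted. If the MMRM is fitted on SS, they would answer an adherence-independent question. The choice of estimand would then follow from the number of visits available, not from a decision about what safety question to ask.

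**Working it through.** No figure in the plan belongs to this point, so the check is a comparison of text, followed by a check of reach and a note on size.

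**1. Data set named for each modelled safety or safety-related measure**

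| Measure | SAP section | Model | Data |
|---|---|---|---|
| Vital signs | 4.6.4 | MMRM | "with all available data in the safety analysis set" |
| Ambulatory blood pressure and heart rate | 4.5, Table GZBF.4.5 | MMRM or ANHECOVA | all available SS data, treatment policy; imputation by treatment group |
| Pancreatic enzymes | 4.6.7.1.1 | MMRM | SS |
| Selected laboratory tests | 4.6.6 | MMRM | none named |
| Selected laboratory tests | 4.6.6 | ANHECOVA | EAS, hypothetical strategy only |

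The ambulatory monitoring row is the closest comparison. It uses the same ANHECOVA, but with SS and imputation from all available data. Pancreatic enzymes are themselves laboratory tests and are on SS. The SAP version history gives, as the reason for a version 3.0 change, that SS should be used for safety parameters. No reason is given for treating the laboratory ANHECOVA differently.

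**2. What the fallback does to the data**

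- SAP 4.3 explains the hypothetical strategy: only data collected before permanent drug discontinuation enter the estimation. A laboratory value observed at a visit after discontinuation is removed and imputed.
- Under SAP Section 3, EAS also removes participants who stopped drug because of inadvertent enrollment. SAP 1.1 keeps them in the safety estimand.
- The laboratory MMRM names no set. If it takes the default of 4.1 and 4.6, it uses SS, and one test can have two estimands depending on the model. If it is read as inheriting the efficacy estimand of 4.3.2, post-discontinuation values are lost there too. Naming SS settles both readings.

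**3. Where the fallback could apply**

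- For SF-36 and the Eating Inventory (SAP 4.7.1.2 and 4.7.1.3), the SAP chooses between MMRM and ANHECOVA by whether there is more than one post-baseline measurement.
- In the Schedule of Activities, hematology and chemistry are sampled at Weeks 8, 12, 24, 36 and 48, so the MMRM is available.
- Calcitonin, cystatin C and urinary albumin/creatinine ratio (UACR) are sampled on treatment after baseline only at Weeks 24 and 48, apart from unscheduled and early-discontinuation samples. At a Week 24 lock each has one scheduled post-baseline visit.
- Whether any of the three is among the selected tests is not stated. For UACR, SAP 4.6.7.8 promises a repeated-measures analysis, which a single visit cannot support.

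**4. Size**

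The documents give neither the share of participants who will be off drug with a laboratory value at the visit, nor the laboratory effect that remains off drug. The form of the gap can be written down. Let q be the share of an active arm off drug, all with observed values, and r the fraction of the on-drug effect that persists off drug. Then

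treatment-policy effect / hypothetical effect = (1 − q) + q·r = 1 − q(1 − r).

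Each dose level randomizes 300 × 2/10 = 60 participants. For assumed q:

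| q (of 60) | r = 0 | r = 0.5 |
|---|---|---|
| 5% (3) | 0.95 | 0.975 |
| 10% (6) | 0.90 | 0.95 |
| 20% (12) | 0.80 | 0.90 |
| 30% (18) | 0.70 | 0.85 |

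These q and r values are assumptions. The table shows how the two estimands separate and does not predict the trial. If people who stop have worse values than those who stay on drug, r exceeds 1 and the gap changes direction.

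**The case against.** The strongest reply is that the SAP allows for this. Both the safety estimand and the SS default carry an exception clause, and 4.6.6 is such a specification. That stands: a reader might infer a strict contradiction, but the text supports only an unexplained exception.

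Other parts of the reply also stand.

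- A reader might infer that every other safety analysis runs irrespective of adherence. It does not: SAP 4.6.7.4 limits hypoglycemia incidence and rates to events before permanent drug discontinuation. The comparison is with the sibling mean-change models.
- A reader might infer that calcitonin, cystatin C and UACR will certainly get this model. The SAP does not list the selected tests. Its calcitonin section plans observed summaries and threshold counts only, it names no analysis for cystatin C, and it promises a repeated-measures model for UACR. The Week 24 lock is itself something that may occur (Protocol 9.5), and by the final lock all three tests have two visits.
- A reader might infer that safety signals are hidden. Visit summaries, shift tables, abnormal-value listings, liver and renal tables and calcitonin categories default to SS. Values taken before discontinuation, including one that prompts stopping, are not excluded by the EAS definition.
- EAS does not drop everyone enrolled inadvertently, only those who stopped drug for that reason.
- An on-drug contrast is a legitimate question. If a laboratory effect fades off drug, the SS contrast is the smaller one, as the table shows for r below 1.

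What the reply does not supply is a reason for making the on-drug contrast the only modelled one for these tests, when the same method in SS is prescribed for ambulatory blood pressure and heart rate.

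**Conclusion.** The point holds as an unexplained and inconsistent exception with limited reach. Where the laboratory ANHECOVA is used as written, observed post-discontinuation values are discarded in favor of on-drug imputations, participants who stopped because of inadvertent enrollment are dropped, and the estimand follows the model.

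No magnitude can be given. A reader might take the planning dropout of 20% and an assumed difference of 0.5 to 1 SD between off-drug and imputed values, giving 0.20 × 0.5 = 0.10 to 0.20 × 1 = 0.20 SD. The documents do not support this. The 20% is failure to complete the study (60 randomized, 48 completing per dose level and placebo). Someone who has left the study has no later value to discard. The relevant share is those who stop drug, stay in the study and attend the visit, and neither that share nor the SD difference is given.

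The conclusion rests on two assumptions: that at least one selected test has too few post-baseline visits for an MMRM at some lock, and that some participants are measured after stopping drug, as Protocol 7.1 intends.

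**What to change.** - In SAP 4.6.6, replace the sentence on the laboratory ANHECOVA with: *The ANHECOVA, if used, will use all available treatment-period data in the SS, with missing values imputed by treatment group.* This follows the ambulatory monitoring rule in Table GZBF.4.5. It also keeps the section's treatment-period limit, which is needed because SS includes follow-up data.
- State SS for the laboratory MMRM in the same section.
- Keep the EAS version with the hypothetical strategy, if wanted, as a supplementary analysis labelled as on-drug.
- List the selected tests, and reconcile the repeated-measures promise for UACR in 4.6.7.8 with its single on-treatment post-baseline visit at a Week 24 lock.

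The core change costs one or two SAP sentences. Sample size, power and alpha are untouched and no data collection changes. It should be made before any further unblinded analysis, because it decides which observed safety values count.

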4.6.7. Additional Safety Assessments

4.6.7.1. Exocrine Pancreas Safety

4.6.7.1.1. *Pancreatic Enzyme*

Observed pancreatic enzyme data (p-amylase and lipase) will be summarized by treatment and nominal visit.

The counts and percentages of participants with maximum postbaseline pancreatic enzyme value exceeding the following thresholds will be provided by baseline pancreatic enzyme value (less than or equal to 1 \times ULN, greater than 1 \times ULN), and treatment: less than or equal to 1 \times ULN, (less than 1 to greater than or equal to 3) \times ULN, (greater than 3 to less than or equal to 5) \times ULN, (greater than 5 to less than or equal to 10) \times ULN, greater than 10 \times ULN. Missing will be considered as a separate group when calculating the counts and percentages.

An MMRM analysis as described in Section 4.3.2 on SS will be used to analyze each pancreatic enzyme with log transformed (postbaseline measure/baseline measure) response variables.

4.6.7.1.2. *Pancreatic Events*

Summaries of adjudicated and investigator-reported pancreatic events will be provided by treatment. Detailed searching criteria can be found in Section 7.6 (Appendix 6).

4.6.7.2. Gastrointestinal Safety

4.6.7.2.1. *Nausea, Vomiting, and Diarrhea*

Summaries and analyses for incidence and severity of nausea, vomiting, diarrhea, and 3 events combined, will be provided by each treatment group.

Summary of the prevalence over time for nausea, vomiting, and diarrhea will also be presented.

Time to the onset of nausea, vomiting, and diarrhea will be plotted. Prevalence and incidence of treatment-emergent nausea, vomiting, and diarrhea will also be plotted.

4.6.7.2.2. *Severe Gastrointestinal Events*

Severe GI AEs (GI SOC) will be captured with AE-CRF form and serious cases will be captured with the SAE form. The PTs in the most updated version of GI SOC MedDRA will be used to identify GI AEs, and only the PTs with serious/severe cases will be considered as AESIs.

The counts and percentages of participants with severe GI events will be summarized by treatment.

4.6.7.3. Hepatic Safety

4.6.7.3.1. *Hepatobiliary Disorders*

Hepatobiliary disorders will be considered as AESIs. The counts and percentages of participants with treatment-emergent potentially drug-related hepatic disorders will be summarized by treatment using the MedDRA PTs. Detailed searching criteria can be found in Section 7.6 (Appendix 6).

- Hepatocellular DILI Screening Plot (TBL versus ALT): Each patient is plotted (ie, scatterplot) based on their maximum postbaseline TBL (y-axis) versus ALT, regardless of the time between the 2 maximum values. Dashed lines represent TBL and transaminase cut-offs of $2 \times$ ULN and $3 \times$ ULN (default) respectively. A potential Hy's Law case is circled and defined as having a maximum postbaseline TBL greater than or equal to $2 \times$ ULN within 30 days after maximum postbaseline ALT or AST greater than or equal to $3 \times$ ULN, without findings of cholestasis (defined as ALP less than $2 \times$ ULN). Include all scheduled and unscheduled laboratory test values.
- Hepatocellular DILI Screening Plot (TBL versus AST): Each patient is plotted (ie, scatterplot) based on their maximum postbaseline TBL (y-axis) versus AST, regardless of the time between the 2 maximum values. Dashed lines represent TBL and transaminase cut-offs of $2 \times$ ULN and $3 \times$ ULN (default) respectively. A potential Hy's Law case is circled and defined as having a maximum postbaseline TBL greater than or equal to $2 \times$ ULN within 30 days after maximum postbaseline ALT or AST greater than or equal to

$3\times$ ULN, without findings of cholestasis (defined as ALP less than $2\times$ ULN). Include all scheduled and unscheduled laboratory test values.

The counts and percentages of participants in each quadrant of the respective plots may be provided by treatment group of LY3437943 and placebo, as shown in [Table GZBF.4.8](#) and [Table GZBF.4.9](#) if data warranted.

Table GZBF.4.8. Summary of Participants with Potential Hepatocellular DILI in LY3437943 Group Versus Placebo

Quadrant	LY3437943 (N=XXX) n (%)	Placebo (N=XXX) n (%)
Potential Hy's Law (Right upper)		
Cholestasis (Left upper)		
Temple's corollary (Right lower)		
Total		

Abbreviations: DILI = drug-induced liver injury; N = number of patients in the analysis population; n = number of patients in the specified category.

Table GZBF.4.9. Summary of Participants with Potential Cholestatic DILI in LY3437943 Group Versus Placebo

Quadrant	LY3437943 (N=XXX) n (%)	Placebo (N=XXX) n (%)
TBL $\geq 2\times$ ULN and ALP $\geq 2\times$ ULN (Right upper)		
TBL $\geq 2\times$ ULN and ALP $< 2\times$ ULN (Left upper)		
TBL $< 2\times$ ULN and ALP $< 2\times$ ULN (Left lower)		
TBL $< 2\times$ ULN and ALP $\geq 2\times$ ULN (Right lower)		
Total		

Abbreviations: ALP = alkaline phosphatase; DILI = drug-induced liver injury; N = number of patients in the analysis population; n = number of patients in the specified category; TBL = total bilirubin; ULN = upper limit of normal.

